	8.3.4 Deviations from the original statistical plan	
9.	DATA AND QUALITY MANAGEMENT	
9.1	Data handling and record keeping / archiving	
9.2	Confidentiality, Data Protection	
9.3	Coding	
9.4	Archiving and Destruction	
10.	PUBLICATION AND DISSEMINATION POLICY	
10.1		
10.2		
	FUNDING AND SUPPORT	.28
	INSURANCE	
13.		
	APPENDICES	

SYNOPSIS (SUMMARY)

(HRO Annex 2/1.1)

Broject London (or	[name] [name]
Project Leader (or Sponsor)	Senior Scientist
opolisoly	Clinical Trial Unit
	[name]
	[name], Switzerland
	[contact]
	e-mail: [contact]
Project Title:	Inspiratory muscle strength and respiratory complications after spinal cord
Project Title:	injury: a multicenter, prospective cohort study
Chart Title / Drainat	RESCOM /2015-14
Short Title / Project ID:	
Project Plan Version and Date:	Version 2, 27.7.2016
Risk categorisation:	Risk category A
Type of Research:	Research project in which health-related personal data will be collected
	and used for further research. Only coded data will be used.
Project design:	Longitudinal, multi-centric cohort study (10 different centers worldwide)
Background and Rationale:	A spinal cord injury (SCI) often leads to paralysis of the respiratory m All data of drop-out patients will be anonymized after analysis. uscles, which causes a decrease in lung capacity and also in the ability to
	cough. Effective coughing is essential for airway clearance. With reduced cough capacity, the risk for pneumonia is increased. Pneumonia is still
	among the leading causes of death in the SCI population and one of the main complications after SCI. In a recent retrospective study of our lab we
	found first evidence that inspiratory muscle strength seems to be a very good discriminator between SCI individuals with and those without pneumonia. Nevertheless, these first results are based on retrospective data of one single center. Additionally, pneumonia is certainly influenced by many other parameters (personal-, lesion- and lifestyle characteristics) and has as well important impacts on e.g. quality of life and mortality. Nevertheless, these relationships are still assumptions which have to be proven in a large prospective cohort study.
Objective(s):	The main objective of this study is to evaluate 'cut-off levels' of inspiratory muscle strength as predictor for pneumonia in individuals with SCI (diagnostic accuracy). Additionally, to evaluate lifestyle and treatment parameters as well as personal- and lesion characteristics as further potential determinants of pneumonia as well as the impact of pneumonia on quality of life and mortality.
Endpoint(s):	Primary study outcome: Diagnostic accuracy of inspiratory muscle strength for prediction of pneumonia. Main secondary study outcomes: Personal- and lesion characteristics, other parameters of respiratory function, lifestyle and treatment parameters, quality of life and mortality
	due to pneumonia.

Inclusion / Exclusion	Inclusion:								
criteria:	Male and female, age ≥ 18 years, AIS A, B, C or D lesion, lesion level C1- T12								
	Exclusion:								
	Neurologic diseases (e.g. MS, ALS), 24h mechanical ventilation								
	dependency, mental disorders								
Project assessments,	Measurements:								
procedures:	- in- and expiratory muscle strength (5min)								
	- lung function (FVC, FEV ₁ , PEF, PCF) (10 min) Questionnaires:								
	- ISCoS core data-set								
	- ISCoS pulmonary function data sets								
	- ISCoS quality of life questionnaire								
	- questionnaire on individual respiratory muscle training, regular physical								
	exercise and therapies								
	- individual medication/vaccination and other medical complications will								
	be assessed from patient's medical records								
	All measurements will be performed at each measurement time-point (up								
	to 4 times during inpatient rehabilitation) and last about 40 min per patient								
	and measurement time-point in total (time with patient).								
Number of	Regarding the in- and exclusion criteria, we made a calculation of a								
Participants:	realistic numbers of subjects who can be recruited for this study per year								
	and center, based on the number of patients admitted to the								
	corresponding center during the last years								
	Estimated numbers of patients per year for each center are as follows:								
	Switzerland: SPZ Nottwil: 30 patients								
	Balgrist Zuerich: 20 patients								
	Rehab Basel: 20 patients								
	CRR Sion: 5 patients								
	Germany: BG Hamburg: 30 patients								
	Austria: Haering: 30 patients								
	Tobelbad: 30 patients								
	Australia: Heidelberg: 40 patients								
	The Netherlands: Rijndam: 20 patients Wijk aan Zee: 20 patients								
	wijk aan zee. zo patients								
	Overall, we will be able to recruit about 250 patients per year for this								
	Overall, we will be able to recruit about 250 patients per year for this study.								
	overall sample size: 625patients								
	With an anticipated number of 625 subjects over a 2.5 years recruitment								
	period, we may detect about 250 cases of pneumonia (under the								
	assumption of a 40% incidence rate).								
Project Duration,	The study is planned to start in October 2016 with the first patients								
schedule:	included. The duration of the whole project will be 2.5 years of								
	recruitment.								
	Month Year of First-Participant-In (planned): October 2016								

Project Centre(s):	Multi-centric project Number of projected centers to be involved: 10 Number of projected countries to be involved: 5 Switzerland:
	 Swiss Paraplegic Centre Nottwil University Hospital Balgrist, Zürich REHAB Basel Clinique romande de réadaptation Sion
	Germany: BG Trauma Hospital Hamburg Austria :
	 Rehabilitationsklinik Tobelbad Rehabilitationszentrum Häring Australia:
	Austin Health, Melbourne The Netherlands:
	 Rijndam Rehabilitation Institute, Rotterdam Heliomare Rehabilitation Center, Wijk aan Zee
Statistical Considerations:	To evaluate the diagnostic accuracy of markers of lung function (particularly MIP) for predicting or excluding clinical pneumonia we wi use contemporary receiver operating characteristic (ROC) analyse techniques that allow for adjusting of covariate effects. Univariable and multivariable regression modelling will be used to evaluate the primar outcome and secondary outcomes. Multivariable modelling as compared univariable modelling will principally allow us to investigate relative contribution of different predictors (or risk factors) to the outcome of interest, while controlling for potential confounding by other factors Multivariable models may further be used to examine effect modification (interaction) as well as mediation.
Other methodological Considerations:	Not applicable
Risk-Benefit statement:	 Risk: Patients have to perform a maximum of 4 measurement sessions (dependent on the time of rehabilitation) with 40 min of measurements each. Therefore the time needed for this study will not negatively influence rehabilitation of included patients. Lung function and respiratory muscle strength measurements are non invasive and also part of clinical routine. Safety of these measurements is very high and to the best of our knowledge we are not aware of any adverse events due to such measurements. Potential benefit of project result: Increased knowledge on determinants and effects of pneumonia will help to adapt rehabilitative strategies/therapy to preven patients from pneumonia and thereby also increase quality of life of the patients and life expectancy.

ABBREVIATIONS

SESerious eventSTROBEStrengthening the reporting of observational studies in epidemiology	AIS AE CA CEC CRF CSC DoH eCRF CTU EC FEV ₁ FVC GCP HFG HRA IMT ISCoS ISO LSC LRH LTI MEP MIP PEF PEP PI ROC SCI	American Spinal Injury Association Impairment Scale Adverse Event Competent Authority (e.g. Swissmedic) Competent Ethics Committee Case Report Form Central Study Coordination Declaration of Helsinki Electronic Case Report Form Clinical Trial Unit Ethics Committee Forced expiratory volume in 1 Second Forced vital capacity Good Clinical Practice Humanforschungsgesetz (Law on human research) Federal Act on Research involving Human Beings Inspiratory muscle trainer International Spinal Cord Society International Organisation for Standardisation Local study coordinators LSC Loi fédérale relative à la recherche sur l'être humain Lower respiratory pressure Maximal expiratory pressure Peak expiratory flow Positive expiratory flow Positive expiratory pressure Principal Investigator Receiver operating characteristic Spinal Cord Iniury
	SCI SE	Spinal Cord Injury Serious event

SCHEDULE OF ASSESSMENTS (FLOW OF RESEARCH PROJECT)

(STROBE #5, 13c)

Time-Table RESCOM Study

	Study set-up (ethics approvals,	local organisation of study sites.	training of study	nurses)	Inpatient setting	(∠.o years or patient	recruitment)	Analysis of	inpatient setting	Paper on	inpatient setting
July 16			il and	24							
Aug 16		1200									
Sep 16	19 79		La Calo			1.1.1					
Oct 16											
Nov 16					-						
Dec 16								-	_		-
Jan 17				-				-	_	-	_
Feb 17											
Mar 17											
Apr 17											_
May 17									-		
June 17											_
July 17									_		
Aug 17				-					_		_
Sep 17				-					-		-
Oct 17									-		_
Nov 17									_		-
Dec 17									_		_
Jan 18								-	-		-
Feb 18									_		_
Mar 18		_							_		_
Apr 18		_		-					_		_
May 18				-				-	-		_
June 18				-		1.81		_	_		
July 16 July 18			_	_					_		_
Aug 18						1.2.5		-	_	_	-
Sep 18				_		192	1	_	_		_
Oct 18	-			_					_		_
Nov 18				_					_	_	_
Dec 18			-	-				-			
									-		_
Jan 19		-	_						_	_	-
Feb 19			_	-				-	-	_	_
Mar 19					1000	100	197	403			-
May 19 Apr 19							_				

Screening	Before T1 T1 T2 T3 T4	post injury (PI) 28±12 84±14 150±18 10 day before	discharge until	Jasion Criteria x	ion and Informed x		×	lication/mortality x x x x	-10) × ×	x x x x	et, pulmonary	d quality of life		dividual	aining, regular	d therapies	X X X X	nuscle strength	, FEV1, PEF,		_		
Project Periods	Visit	Time-frame in days post injury (PI)		Screening: In- /Exclusion Criteria	Participant Information and Informed	Consent	Demographics	Medical History/medication/mortality	Co-morbidities (ICD-10)	Questionnaires:	- ISCoS core data set, pulmonary	function data set and quality of life	data set	 questionnaire on individual 	respiratory muscle training, regular	physical exercise and therapies	Tests:	- in- and expiratory muscle strength	- lung function (FVC, FEV1, PEF,	DCF)			

RESCOM, Version 2 of 27.7.2016

2. ETHICAL AND REGULATORY ASPECTS

2.1 Ethical Conduct of Study (HRA Art. 45-49; HRO, Art. 14, 17-23, Annex 2)

This research project will be carried out in accordance to the research plan and with principles enunciated in the current version of the Declaration of Helsinki (DoH), the Essentials of Good Epidemiological Practice issued by Public Health Schweiz (EGEP), the Swiss Law and Swiss regulatory authority's requirements as applicable. The EC and regulatory authorities will be informed about project start and termination.

2.2 Risk categorisation (HRO Art. 7, 33)

Our project corresponds to the Category A involving persons.

The measurement of respiratory muscle strength parameters represents no risk for the study participants. Apart from the determination of respiratory muscle strength, only one additional questionnaire will be performed during the course of this study (see 7.1 Project Flow Chart).

2.3 Ethics Committee (EC) and Competent Authorities (CA), FOPH (HRO Art. 14-23, 34, 37, 41, 45)

All project-specific documents will be submitted to a Ethics Committee before the project will be conducted.

The responsible investigator at each site ensures that approval from an appropriately constituted Competent Ethics Committee (CEC) is sought for the study.

No changes are made to the protocol without prior Ethic Committee and Sponsor approval, except where necessary to eliminate apparent immediate hazards to study participants. All changes in the research activity and all unanticipated problems will be reported to the CEC.

Premature study end or interruption of the study is reported within 15 days. The regular end of the study is reported to the EC within 90 days, the final study report shall be submitted within one year after study end.

2.4 Participant Information and Informed Consent (HRO Art. 8, Annex 2/1.3-1.5)

The investigators or study nurses of each participating site will explain to each participant the nature of the study, its purpose, the procedures involved, the expected duration, the potential risks and benefits and any discomfort it may entail. Each participant will be informed that the participation in the study is voluntary and that he/she may withdraw from the study at any time and that withdrawal of consent will not affect his/her subsequent medical assistance and treatment.

The participant must be informed that his/her medical records may be examined by authorised individuals other than their treating physician.

All participants for the study will be provided a participant information sheet and a consent form describing the study and providing sufficient information for the participant to make an informed decision about their participation in the study. Enough time (a minimum of 24hours) needs to be given to the participant to decide whether to participate or not.

The patient information sheet and the consent form will be submitted to the CEC and to the competent authority (as applicable) to be reviewed and approved. The formal consent of a participant, using the approved consent form, must be obtained before the participant is submitted to any study procedure.

The participant should read and consider the statement before signing and dating the informed consent form, and should be given a copy of the signed document. The consent form must also be signed and dated by the investigator (or his designee) and it will be retained as part of the study records.

See also Chapter 3.3 Risk-benefit assessment.

2.5 Participant privacy and safety (HRA Art. 1, Annex 2/1.7)

The Project Leader affirms and upholds the principle of the participants' right to dignity, privacy and health and that the project team shall comply with applicable privacy laws. Especially, anonymity of the participants shall be guaranteed when presenting the data at scientific meetings or publishing them in scientific journals.

Individual participant medical information obtained as a result of this research project is considered confidential and disclosure to third parties is prohibited. Participant confidentiality will be further ensured by utilising identification code numbers to correspond to medical information in the computer files.

For data verification purposes, authorised representatives of the Sponsor, a competent authority (e.g. FOPH), or an ethics committee may require direct access to parts of the medical records relevant to the project, including participants' medical history.

2.6 Early termination of project (HRO Art. 22)

The sponsor, the project leader or the coordinating researcher may terminate the study prematurely according to certain circumstances, for example:

- ethical concerns,
- insufficient participant recruitment,
- when the safety of the participants is doubtful or at risk, respectively,
- · alterations in accepted clinical practice that make the continuation of a clinical trial unwise,
- early evidence of benefit or harm of the experimental intervention

The premature end or interruption of the research project is reported to the EC within 90 days upon completion of the project.

2.7 Amendments, Changes (HRO Art. 18, 22, Annex 2)

Substantial amendments are only implemented after approval of the CEC.

All Non-substantial amendments are communicated to the CEC within the Annual Safety Report (ASR).

3. INTRODUCTION

(STROBE 2; HRO Annex 2/1.2)

3.1 Background

A spinal cord injury (SCI) often leads to paralysis of respiratory muscles (1), which causes a decrease in inspiratory volume and consequently limits the pre-cough volumes needed to produce an effective cough (2). The ability to cough is essential for airway clearance (3). With reduced cough capacity, the risk for pneumonia is increased (1). Pneumonia is still among the leading causes of death in the SCI population (4, 5). In acute SCI, up to 80% of patients are affected by respiratory complications (6) and in 51% of these cases pneumonia occurs (7), corresponding to a cumulative pneumonia incidence rate of about 40%. Unfortunately, predictors of pneumonia in SCI are still poorly understood (6).

To our knowledge, there are three studies on predictors of pneumonia in the SCI population (8, 9). Two of these studies concentrated on factors of injury and shock severity (9) or identified the level and completeness of injury as the fundamental clinical entity predicting pulmonary complications (8). However, both studies did not investigate potentially modifiable factors. The third study focused on potentially modifiable factors, such as lung function but did not cover respiratory muscle strength and did not define the inclusion of respiratory complications precisely (10). Therefore, to facilitate future evidence-based strategies to reduce the pneumonia risk in acute SCI, prevention targeted studies that aim to identify modifiable risk factors for pneumonia are urgently needed.

The current research proposal is targeted at specific parameters of respiratory function that are conceivably determinants of pneumonia risk as well as modifiable by respiratory muscle training (11, 12). In a recent study (accepted for Publication, Respiratory Care) we evaluated various respiratory function parameters and identified inspiratory muscle strength as a reliable discriminator between individuals with and those without pneumonia.

Although we identified inspiratory muscle strength as best parameter of respiratory function to discover individuals with SCI at risk for pneumonia, these data are based on a retrospective singlecenter data analysis without any detailed information on the type, time-point and severity of pneumonia. Also data on mortality due to pneumonia and other personal parameters that may influence the risk for pneumonia as well (e.g. smoking, exercise, mechanical ventilation dependency etc.) are missing in this analysis.

3.2 Rationale for the research project

To determine diagnostic accuracy of our concept of using 'cut-off levels' for inspiratory muscle strength to predict pneumonia in the management of SCI, replication in a large longitudinal multi-center cohort study is essential. Only a multi-center study may allow a larger sample size and the increase in power needed for an in-depth analysis of generalizability of and variation in 'cut-off levels' across settings and patient groups.

3.3 Risk-Benefit Assessment (HRA Art. 12; HRO Art. 15)

Patients have to perform a maximum of 4 measurement sessions (dependent on the time of rehabilitation) with 40 min of measurements each. Therefore the time needed for this study will not negatively influence rehabilitation of included patients. Lung function and respiratory muscle strength measurements are non-invasive and also part of clinical routine. Safety of these measurements is very high and to the best of our knowledge we are not aware of any adverse events due to such measurements.

Potential benefit of project result:

Increased knowledge on determinants and effects of pneumonia will help adapt rehabilitative strategies/therapy to prevent patients from pneumonia and thereby also increase quality of life of the patients and life expectancy.

4. OBJECTIVES, ENPOINTS/OUTCOMES AND OTHER STUDY VARIABLES

4.1 Objectives (STROBE 3)

The primary objective of the study is to evaluate diagnostic accuracy of 'cut-off levels' for inspiratory muscle strength as predictor for pneumonia in individuals with SCI.

Specific aims include:

1) to evaluate lifestyle and treatment parameters as well as personal- and lesion characteristics as potential other determinants for pneumonia;

2) to evaluate the association between pneumonia and quality of life as well as mortality due to pneumonia.

4.2 Primary and secondary endpoint/outcome(s) (STROBE #7)

Primary endpoint: Inspiratory muscle strength in relation to pneumonia

Secondary endpoints:

- mortality due to pneumonia
- quality of life
- other respiratory function parameters

Potential explanatory variables:

- personal and lesion characteristics (gender, age, height, weight, lesion level, AIS grade etc.)
- smoking status
- partly mechanical ventilation dependency
- medication and vaccination
- respiratory muscle training and physical exercise

4.3 Other study variables (STROBE #7)

not applicable

5. PROJECT DESIGN

(STROBE 4,5, 9; HRO Annex 2/1.2)

5.1 Type of research and general project design (STROBE 4)

Longitudinal, multi-centric cohort study (10 different centers, international)

5.2 Procedures (STROBE 5; swissethics 3a)

During inpatient rehabilitation 4 measurement time-points (T1-T4) will be used to assess longitudinal data of each participating patient.

Measurements:

- in- and expiratory muscle strength (5min)
- lung function (FVC, FEV1, PEF, PCF) (10min)

Questionnaires:

- ISCoS core data-set (5min)
- ISCoS pulmonary function data sets (5min)
- ISCoS quality of life questionnaire (5min)
- questionnaire on individual respiratory muscle training, regular physical exercise and therapies (5-10min)

Individual medication/vaccination and other medical complications will be assessed from patient's medical records.

All measurements will be performed at each measurement time-point and last about 40 min per patient and measurement time-point in total (time with patient).

For the study nurse time needed per patient and measurement time-point (including planning, preparation, documentation and data entry) will be about 90 min.

5.3 Recruitment and Screening (swissethics 3b)

During a consecutive enrollment all patients, who fulfill the inclusion criteria, will be asked for participation by a skilled study nurse.

Screening tests:

- demographic data (age, language)
- severity and level of the lesion
- exclusion criteria

5.4 Methods of minimising bias (STROBE 9; swissethics 2)

Throughout the study, the coding of the participants will be conducted by the study nurses of each site in order to keep the data management and the biostatistician blind against the study condition as long as the data bank is open. The coding list remains with the study nurses of each site for the whole duration of the study. Thus, coding will be conducted without any influence of the principal investigator or raters.

The study investigators will strive for complete separation of the individuals involved in the steps before enrolment from those involved in the data management and analysis.

Assessments of primary and secondary outcomes will be conducted by a study nurse without any influence on data analysis. All study nurses will go through a profound assessment training program. A study nurse will enter data into the secuTrial[®] data management system so that the biostatistician can analyze the data without having access to information about the origin, or names of participants.

6. PROJECT POPULATION

(STROBE 6; HRO Annex 2/1.2)

6.1 Inclusion criteria

Initial rehabilitation after SCI, men and women, age ≥ 18 years, AIS A, B, C or D lesion, lesion level C1-T12

6.2 Exclusion criteria

Neurologic diseases (e.g. MS, ALS), 24h mechanical ventilation dependency, mental disorders

6.3 Criteria for withdrawal / discontinuation of participants

Reasons for which a participant needs to discontinue from the project:

- withdrawal of informed consent
- non-compliance
- medical complications which do not allow measurements of this study
- death

In case of drop-out, the already recorded data will be used for further analyses. All data of drop-out patients will be anonymized after analysis.

We will report all reasons for withdrawal of the participants and compare the reasons qualitatively.

The study will not be stopped in case of futility, unless CTU Nottwil during the course of safety monitoring advices otherwise. In this case, CTU Nottwil will discuss potential stopping for futility with the study investigators group.

The final decision to terminate the study is taken by the Principal Investigator of the study.

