7.1 Project flow chart(s) / table of procedures and assessments

7.2 Assessments of primary endpoint/outcome

The primary endpoint of this study is the diagnostic accuracy of inspiratory muscle strength for predicting or excluding clinical pneumonia. Diagnostic accuracy of positive and negative results will be evaluated by the area under the receiver operating characteristic (ROC) curve, which provides an operational measure of the intrinsic ability of the diagnostic test by offsetting the true positive rate against the false positive rate (13). Based on our previous evidence, MIP was defined as the primary diagnostic lung parameter (14). The potential additive diagnostic value of various other lung parameters, including forced vital capacity (FVC), forced expiratory volume in 1 second (FEV₁), peak expiratory flow (PEF), peak cough flow (PCF) and maximum expiratory muscle strength (MEP) will also be investigated. The two measures for the primary endpoint, maximal inspiratory pressure (MIP) and the event of clinical pneumonia, are assessed as follows.

Inspiratory muscle strength will be measured using a hand-held respiratory pressure meter (Micro RPM, Micro Medical, Hoechberg, Germany) by an independent study nurse of each participating study site. All measurements will be performed with the patients sitting upright in their own wheelchair. Patients have to breathe through a mouthpiece while wearing a nose clip. Each measurement will be repeated three times. The greatest value of each parameter will be used for analysis (15).

For each event of pneumonia the following information will be recorded: date of event; duration of event; physician diagnosed; and type. The differentiation of the type of pneumonia is important and will be evaluated using patients medical records data following the pneumonia flow diagram of "Disease and Control Prevention / National Healthcare Safety surveillance definition of health care—associated infection and criteria for specific types of infections in the acute care setting" (16). To determine the type of pneumonia the methods x-ray, signs and symptoms and the laboratory are used. Finally four different types of pneumonia can be diagnosed.

Pneumonia 1: clinically defined pneumonia

Pneumonia 2: pneumonia with common bacterial or filamentous fungal pathogens and specific lab findings

Pneumonia 3: pneumonia with viral and other uncommon pathogens and specific lab findings Pneumonia 4: pneumonia in immunocompromised patients

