7.3 Assessment of secondary endpoint/outcome(s)

Secondary endpoints of this study include the various lung parameters mentioned above; other medical complications; quality of life; co-morbidities, medication and vaccination and mortality, in particular pneumonia-related death.

The various lung parameters thus include maximal inspiratory pressure (MIP), maximum expiratory pressure (MEP), vital capacity (FVC), forced expiratory volume in 1 second (FEV₁), and peak expiratory flow (PEF).

The peak cough flow (PCF) will be measured by having the person cough as forcefully as possible through a peak flow meter.

Medical complications will be assessed from the patient's medical records by the study nurse without involvement of the patient.

Quality of life (QoL) will be evaluated using the Quality of Life Basic Data Set of the International Spinal Cord Injury Datasets. This measurement instrument accepts (QoL) as a multi-facetted concept and includes three questions as to capture general quality of life (overall well-being), rating of physical health, and satisfaction with psychological health (17).

Co-morbidities will be assessed only once using the ICD-10 codes after the end of inpatient rehabilitation. This will also be assessed from the patient's medical records by the study nurse without involvement of the patient.

Medication and vaccination will be assessed at each measurement time-point (T1-T4) from the patient's medical records by the study nurse without involvement of the patient.

Mortality will be defined as pneumonia-related, if a prevailing event of pneumonia was clinically resolved as the initiating factor of the cascade of morbid events leading directly to death. Similarly, other causes of death will be recorded as part of all-cause mortality and as potentially competing risks of death.

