8. STATISTICAL METHODOLOGY

8.1 Determination of Sample Size (STROBE 10)

Regarding the in- and exclusion criteria, we made a calculation of a realistic numbers of subjects who can be recruited for this study per year and center, based on the number of patients admitted to the corresponding center during the last years.

Estimated numbers of patients per year for each center are as follows:

Switzerland:	SPZ Nottwil:	30 patients
	Balgrist Zürich:	20 patients
	Rehab Basel:	20 patients
	CRR Sion:	5 patients
Germany:	BG Hamburg:	30 patients
Austria:	Haering:	30 patients
	Tobelbad:	30 patients
Australia:	Heidelberg:	45 patients
The Netherlands:	Rijndam:	20 patients

Heliomare: 20 patients

Overall, we will be able to recruit about 250 patients per year for this study.

Overall sample size: 625 patients

With an anticipated number of 625 subjects over a 2.5 years recruitment period, we may detect about 250 cases of pneumonia (under the assumption of a 40% incidence rate (6, 7).

Moreover, taking the diagnostic accuracy (i.e., area under the curve (AUC)) of 0.86 from a retrospective study as reference (14), the envisioned sample size of at least 250 cases per diagnostic group should allow for detecting a diagnostically and clinically relevant effect (i.e., change in AUC) of 0.07 to 0.05 with 95% confidence level and 80% power (18).

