8.3.1 Descriptive analysis

Descriptive statistics involving demographic data, lesion characteristics, life style characteristics, medication and vaccination, partly mechanical ventilation dependency, smoking, respiratory muscle

training and physical exercise as well as primary and secondary outcome parameters will be presented as mean (standard deviation) and median (25% and 75% quartile) or frequency (binomial 95% confidence interval), where appropriate. Descriptive statistics will be provided for the overall sample as well as stratified for the two groups that are discriminated by the event of at least one event of pneumonia during the study period.

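### Section 6.3 ends participation for non-compliance or complications that prevent the measurements, without saying that pneumonia and death are still collected from records

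*Combined protocol and SAP*

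**What the plan says.** Section 6.3 introduces its list with "Reasons for which a participant needs to discontinue from the project". The list has four entries: withdrawal of consent, non-compliance, "medical complications which do not allow measurements of this study", and death. The wording is mandatory and concerns the project as a whole, not a single visit. The only rule on data is "In case of drop-out, the already recorded data will be used for further analyses"; those data are anonymised after analysis. Reasons for withdrawal are to be reported.

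The outcomes do not depend on the patient performing a test:

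- Section 7.2: the type of pneumonia "will be evaluated using patients medical records data following the pneumonia flow diagram".
- Section 7.3: "Medical complications will be assessed from the patient's medical records by the study nurse without involvement of the patient".
- Section 7.3: "Co-morbidities will be assessed only once using the ICD-10 codes after the end of inpatient rehabilitation".
- The visit table in section 7 lists mortality with medical history at T1 to T4.

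The analysis sections presume follow-up over the whole stay. The descriptive analysis (8.3.1) forms two groups "discriminated by the event of at least one event of pneumonia during the study period". The mortality analysis (8.3.2) ends survival time at discharge or death. It treats other causes of death and transfer as possible competing risks, and does not mention discontinued participants.

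**The concern.** Section 6.3 does not separate the end of testing from the end of outcome collection, and it does not say whether temporary inability counts. A site could reasonably stop extracting records once a patient is discontinued. A pneumonia recorded before exit would be kept, but a first pneumonia or a death after exit might not be.

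The loss would not be random. Complications severe enough to prevent testing may precede pneumonia or death, and may go with weak inspiratory muscles, so loss can depend on both the marker and the outcome. Most exposed are mortality, which is a secondary endpoint (4.2) and the subject of one of three planned papers (10.1), and pneumonia incidence. The plan also does not say how leavers with unknown outcome enter the ROC analysis.

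**Working it through.** **The plan's own figures (8.1).** 250 patients per year × 2.5 years = 625, and 625 × 0.40 = 250, in line with "we may detect about 250 cases of pneumonia". With 250 per group, a reference AUC of 0.86, two-sided 5% and 80% power, the binormal variance formula gives a detectable increase of 0.067 (two independent AUCs) or 0.051 (one AUC against a fixed value). This matches the stated 0.07 to 0.05.

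**Assumed inputs.** The documents give no drop-out rate, death rate or timing. Drop-out here means exits for medical complications or non-compliance only.

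- Drop-out: 5, 10 or 20%.
- MIP: binormal with AUC 0.86, so group separation √2 × z(0.86); 40% cases.
- Exit: unrelated to anything; odds ratio 2 per SD of lower MIP; odds ratio 2 for cases; both; or odds ratio 2 per SD of lower MIP in cases only.
- First pneumonia falls after exit in 25, 50 or 100% of leavers who become cases.

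**Cases lost, of 250** (simulation of 1,000,000 subjects, scaled to 625):

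| Drop-out | Cases lost |
|---|---|
| 5% | 3–23 |
| 10% | 6–45 |
| 20% | 13–85 |

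Simplest check at 10%: exit unrelated and 25% of first pneumonias after exit gives 250 × 0.10 × 0.25 = 6.25.

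**Observed pneumonia proportion at 10% drop-out** (true 40%): about 36 to 42% if leavers without a recorded pneumonia are excluded, and about 39 to 41% if they are imputed from MIP. It can move either way because leavers with an earlier recorded pneumonia stay in.

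**Share of deaths unrecorded** (rare-event approximation) = f·RR·s / (f·RR·s + 1 − f). Here f is drop-out, RR is the leavers' later death rate relative to stayers, and s is the share of the stay after exit. At f = 0.10:

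| RR | s = 0.5 | s = 1 |
|---|---|---|
| 1 | 0.05/0.95 = 5% | 0.10/1.00 = 10% |
| 2 | 0.10/1.00 = 10% | 0.20/1.10 = 18% |
| 4 | 0.20/1.10 = 18% | 0.40/1.30 = 31% |

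**Primary AUC at 10% drop-out** (true 0.86):

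| Leavers with unknown outcome | AUC |
|---|---|
| Excluded, odds ratios up to 2 | 0.850–0.865 |
| Imputed from MIP, odds ratios up to 2 | 0.855–0.864 |
| Excluded, odds ratios of 4 | down to 0.838 |
| Coded as non-cases, odds ratios up to 2 | 0.794–0.854 |

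**Precision.** The worst losses at 10 and 20% leave 250 − 45 = 205 and 250 − 85 = 165 cases. Against 375 non-cases and a fixed 0.86, the detectable change is 0.052–0.057 and 0.056–0.062, inside the stated 0.05 to 0.07.

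**The case against.** Silence is not prohibition. Section 6.3 nowhere bars further record review, and other text leans towards follow-up to discharge: mortality at every visit, co-morbidities taken from records after rehabilitation, survival ending only at discharge or death. The consent text and the data manual named in 8.2 were not available for this review and may settle the matter. This stands as a limit: the defect is an omission and a mismatch between 6.3 and 8.3.2. None of those passages expressly covers a discontinued participant.

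The plan also has safeguards. Section 8.3.2 checks attrition against baseline characteristics and allows inverse probability weighting for longitudinal attrition. The section on datasets to be analysed plans multiple imputation and missForest, and the ancillary analysis compares imputed with complete data. These may reduce bias. But the weighting is optional, the attrition check looks at baseline while this exit reason arises later, and no model recovers an unrecorded death.

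A reader might infer that anyone who fails a breathing test must leave. The text does not say so. Apart from non-compliance, it covers only medical complications that prevent the measurements, and 5.2 uses that word both for the breathing tests and for the whole 40-minute session.

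Finally, all sizes are assumed. The upper case losses need every first pneumonia among leavers to fall after exit, and a share of deaths without a death count does not show how many deaths are at stake. Both limits stand.

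**Conclusion.** The gap is real and cheap to close. Section 6.3 mandates exit and secures only earlier data, while 8.3.1 (descriptive analysis) and 8.3.2 presume outcomes over the study period, to discharge or death. The main exposure is mortality and pneumonia incidence. At an assumed 10% drop-out, about 6 to 45 of 250 cases are lost (odds ratios up to 2), and about 5 to 31% of deaths go unrecorded (rate ratios 1 to 4, exit between the start and the middle of the stay).

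Two stronger readings are not supported. One is that the primary AUC is seriously compromised. With leavers of unknown outcome excluded, bias is about 0.01 at 10% drop-out if odds ratios do not exceed 2. That is not a bound, since odds ratios of 4 bring the AUC down to about 0.84. The larger distortion needs such leavers coded as non-cases, and the plan neither states nor excludes this. The other is that the sample size fails: precision stays within the stated range in every odds-ratio-2 scenario tried. This is a recommended improvement, not a fatal flaw.

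**What to change.** - Amend 6.3 so that inability to perform the tests, or non-compliance with them, ends only the tests. State whether temporary inability counts.
- Continue extracting pneumonia events, transfer or discharge, and death with cause from records until discharge unless consent is withdrawn, after checking that the consent text covers this, especially for non-compliant participants.
- Reconcile 8.3.2 with 6.3 by stating how discontinued participants are censored.
- State that leavers with unknown outcome are not coded as non-cases.

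Cost: protocol wording and modest record extraction by nurses who already do this work. Section 5.2 gives about 90 minutes of nurse time per time-point, about 40 of them with the patient, which leaves at most 50. At an assumed 10% drop-out with three missed time-points each, 62.5 × 3 × 50 min = 9,375 min, about 156 hours in all or 16 per centre over ten centres. The consent wording may need amending, and records may be unavailable after transfer. A leaver who never performed MIP still adds nothing to the ROC analysis; the records then serve incidence and mortality only.
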